Statistical Analysis: [name] will supervise the data analyses for this proposal along with [name] and all analyses will be performed using SAS software, version 9.4 (SAS Institute, Inc., Cary, NC). The primary analyses will be done using intention-to-treat methods. We will compare the two groups on baseline characteristics to assess the adequacy of the randomization. Baseline characteristics include analgesic use, age, number of comorbidities, body mass index, gender, and race/ethnicity). If statistically or clinically significant between-group differences are noted, we will conduct sensitivity analyses controlling for the unbalanced variables to assess the impact on the inference for the treatment groups. Prior to conducting all of the statistical analyses outlined below, we will evaluate the assumptions of the statistical models and outliers and influential cases will be screened for and removed. All tests will be two sided with type I error of 5%. In order to reduce type I errors, secondary outcomes will be examined using an alpha = .01.

Aim 1: Primary Hypothesis. Following 8 weeks of treatment, a greater improvement in LBP-related disability and physical function (as measured by change in Quebec LBP Disability score and self-selected gait speed, respectively) will be observed for individuals that receive HIP+ compared to spine-focused rehabilitation (SFR).

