Quebec score and gait speed will be used to test our specific hypotheses about short-term (immediately post-treatment) and longer-term (6-months post-randomization) changes in disability and pain severity. We will use linear mixed models with time (baseline, 8 weeks and 6 months) and the group*time interaction as fixed effects while controlling for repeated measures using an unstructured correlation matrix between time points. The effect of time will be treated as categorical. No main effect for treatment is included as the baseline means are assumed and constrained to be equal due to randomization. We will also control for site and sex as fixed effects since these are stratification factors in the randomization. We will use linear contrasts to test HIP+ versus SFR at 8 weeks and 6 months (Aim 1). GLMM assumptions include homoscedasticity, normality, and linearity using standard graphical methods, the Shapiro-Wilk test, and Box-Cox test respectively. If model assumptions are violated, we will consider transformations (e.g. Box-Cox method) that can be applied but maintain interpretability. We will test the secondary outcome measures related to Aim 1 in the same fashion to identify which outcomes should be considered in future trials.

The rates of individual adverse events and serious adverse events that occur >10% and adverse events classified by organ system and relatedness will be calculated for each group and compared using Chi-square or Fisher's exact tests.

Aim 2: Hypothesis. Reductions in hip joint pain, increases in hip strength and increases in functional self-efficacy will be associated with improvements in LBP-related disability and physical function.

Two sets of regression analyses will be used to determine the degree to which changes in hip pain, hip strength and functional self-efficacy explain changes in LBP-related disability and physical

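### Does leaving out the treatment main effect fail to hold the two baseline means equal in the primary mixed model?

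*Combined protocol and SAP*

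**What the plan says.** The Aim 1 analysis is set out in Section 10 (DATA), under the question on how data will be analysed and reported. The fixed effects are given as follows: "We will use linear mixed models with time (baseline, 8 weeks and 6 months) and the group*time interaction as fixed effects". On coding, the text adds: "The effect of time will be treated as categorical". The baseline is dealt with in one sentence: "No main effect for treatment is included as the baseline means are assumed and constrained to be equal due to randomization".

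The covariance is specified as "controlling for repeated measures using an unstructured correlation matrix between time points", and site and sex are added as fixed effects. HIP+ and SFR are then compared by linear contrasts at 8 weeks and at 6 months. The primary hypothesis is worded in terms of change: "as measured by change in Quebec LBP Disability score and self-selected gait speed, respectively". On software, the plan says that "all analyses will be performed using SAS software, version 9.4". It gives no procedure, model statement, reference level or contrast coding.

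**The concern.** The plan presents the missing treatment term as the way the baseline means are made equal. With a three-level categorical time factor that includes baseline, a fully coded interaction carries a group difference at every visit, baseline among them. Dropping the main effect then removes nothing: its degree of freedom moves into the interaction and the fit still has two baseline means. SAS, with both factors declared as classification variables, would run this without a warning.

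Baseline adjustment in the primary comparison would be at stake. In the unconstrained fit with complete data, the 8-week contrast is the plain difference in 8-week means, allowing for site and sex. Subtracting the baseline difference gives a change-score contrast instead. Either is less efficient than the constrained model, and both let a chance baseline imbalance into the estimate. Secondary outcomes are to be analysed in the same way, so a coding slip would reach them too.

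**Working it through.** **Inputs.** From the documents: 180 participants allocated equally, so 90 per arm; three visits; two-sided 5% tests; site and sex as covariates. Assumed, because the documents give no value: SD of 1, the same correlation ρ between all visits, complete data. The plan states no power, target difference or SD, so there is no figure of its own to reproduce.

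**Step 1: what each coding fits.** Two groups at three visits give six cell means.

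| Coding of time and group | Rank | Rank with site and sex |
|---|---|---|
| Time + group + interaction | 6 | 9 |
| Time + interaction, all three visits kept, no group term | 6 | 9 |
| Time + interaction at 8 weeks and 6 months only, no group term | 5 | 8 |

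Putting the columns of the first two designs together still gives rank 9, so they are the same model. The third has 3 visit means plus 2 treatment differences, hence a single baseline mean. Its time factor is also categorical. The constraint therefore depends on which interaction columns are kept, not on whether time is categorical or continuous.

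**Step 2: cost if all three interaction levels were kept.** Variances of the 8-week group difference:

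- Constrained: (2/90)(1 − ρ²)
- Unconstrained, at the visit: 2/90 = 0.0222, SE 0.149
- Unconstrained, change from baseline: (2/90) × 2(1 − ρ)

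The variance ratios R to the constrained model are 1/(1 − ρ²) at the visit and 2/(1 + ρ) for change. For an effect with 80% power under the constrained model, power becomes Φ((1.960 + 0.842)/√R − 1.960).

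| ρ | SE, constrained | R, at visit | Power, at visit | R, change | Power, change |
|---|---|---|---|---|---|
| 0.3 | 0.142 | 1.10 | 76% | 1.54 | 62% |
| 0.5 | 0.129 | 1.33 | 68% | 1.33 | 68% |
| 0.6 | 0.119 | 1.56 | 61% | 1.25 | 71% |
| 0.7 | 0.107 | 1.96 | 52% | 1.18 | 73% |
| 0.8 | 0.089 | 2.78 | 39% | 1.11 | 76% |

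Worked line at ρ = 0.5: R = 1/(1 − 0.25) = 1.33; 2.802/1.155 − 1.960 = 0.466; Φ(0.466) = 0.68.

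**Step 3: chance imbalance.** Take no treatment effect and a baseline difference of 0.2 SD. The expected estimate is 0 in the constrained model, 0.2ρ for the at-visit contrast and −0.2(1 − ρ) for the change contrast. At ρ = 0.5 these are 0, +0.10 and −0.10 SD. Averaged over randomisation the imbalance is zero, so all three estimators are unbiased with complete data.

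**Step 4: at-visit or change?** With a common baseline mean b, the difference in change is (HIP+ mean − b) − (SFR mean − b), which is the at-visit difference. In the model the plan describes, the change wording of the hypothesis and the at-visit wording of the contrasts name the same quantity.

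**The case for a change.** The strongest case for a change is that the plan names one mechanism for the constraint, omission of the main effect, and in the named software's usual classification coding that mechanism does not work. Nothing would flag the error. The at-visit and change contrasts would then differ, and under a 0.2 SD imbalance at ρ = 0.5 they point in opposite directions. An imbalance that large is not rare: 0.2/0.149 = 1.34 standard errors, a two-sided probability of about 18%. The planned check of baseline characteristics lists neither Quebec score nor gait speed, so it would not catch the problem. A sentence on coding would cost almost nothing.

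The algebra in this stands: omission alone is not enough when all interaction levels are kept, and the text would be tighter if it named the columns. What does not stand is the step to a faulty primary analysis. The equality of the baseline means is stated as a feature of the model, so an analyst who found two baseline means in the output would see that the fit was not the one specified. The power losses are those of a program that nobody has written, at correlations the documents do not give. The two-contrast ambiguity exists only in that unconstrained fit.

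**Conclusion.** The concern does not call for a change. Categorical time, an interaction, no treatment main effect, an unstructured matrix and an explicit common baseline together describe a constrained longitudinal model, which is a sound primary analysis for this design. The paragraph leaves out which interaction columns carry the constraint. The constraint itself answers that: those for 8 weeks and 6 months. Writing the coding down would describe the same model and would alter no estimate, test or sample size.

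The losses in the table (power of 39% to 76% in place of 80%, over ρ from 0.3 to 0.8) apply only if the program ignores the stated constraint. They also rest on complete data, equal correlations and an assumed ρ. Even then, with complete data, the contrasts would be unbiased over randomisation; the cost would be precision and protection against chance imbalance.

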1. Explore whether a hip-focused treatment leads to reduced disability and improved physical function when compared to a low back-focused treatment in an at-risk hip-spine subgroup (i.e. those with both hip pain and weakness, in addition to low back pain).
2. Determine what contributes to improvements in disability and physical function in this at-risk hip-spine subgroup.

6. PROCEDURES Describe all procedures involving human subjects for this protocol. Include copies of all surveys and research measures.

Study Participants.

Participants with moderately intense (LBP rated at least 4/10), chronic LBP (pain of at least 3 months) that impacts daily activities with concurrent hip pain and hip weakness will be recruited from newspaper and online advertisements, as well as from databases of former study participants who have agreed to be contacted for future studies. The sample will be recruited from one of three areas in this multi-site clinical trial: Newark, DE and surrounding communities, Pittsburgh, PA and surrounding communities and Durham, NC and surrounding communities.

Design and Randomization Plan.

In total, 180 participants meeting the inclusion/exclusion criteria will be randomly assigned into one of two intervention groups: (1) spine treatment supplemented with a hip-focused manual therapy and hip-focused exercise intervention, or (2) spine-focused rehabilitation with stationary cycling. We will use statistical software to generate a randomization plan that ensures by the end of the study that an equal number of participants are randomly assigned to each of the two treatment conditions. We will perform randomization separately in men and women given the reported sex differences in pain conditions among older adults²⁵, this approach will ensure equal randomization of men and women into both randomization groups. The treatment assignments will be uploaded into the web-based data entry application for the study. A participant's study allocation will be revealed to approved study personnel (i.e. not physical therapy testers) once all eligibility criteria have been entered and eligibility is confirmed.

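### Site and sex enter the repeated-measures model without a time interaction, so differences in improvement by site or sex are only partly adjusted for and the reported standard error is slightly too large

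*Combined protocol and SAP*

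**What the plan says.** Section 10 (DATA), Statistical Analysis, Aim 1, sets out one model for the Quebec score and gait speed: "We will use linear mixed models with time (baseline, 8 weeks and 6 months) and the group*time interaction as fixed effects", "controlling for repeated measures using an unstructured correlation matrix between time points", with time categorical. Baseline is therefore a response, and the arms are held equal there: "No main effect for treatment is included as the baseline means are assumed and constrained to be equal due to randomization". The arms are then compared by linear contrasts at 8 weeks and at 6 months.

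The covariates come in one sentence: "We will also control for site and sex as fixed effects since these are stratification factors in the randomization". The interaction with time is written out for treatment group. None is written for site or sex, here or anywhere else in the document. Secondary outcomes follow the same model: "We will test the secondary outcome measures related to Aim 1 in the same fashion".

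Two other places bear on the point. Section 6 (PROCEDURES), Design and Randomization Plan, describes stratification by sex only: "We will perform randomization separately in men and women given the reported sex differences in pain conditions among older adults". The opening paragraph of the Statistical Analysis provides sensitivity analyses for baseline characteristics that turn out unbalanced. Gender is on that list, site is not, and no time interaction is mentioned.

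**The concern.** In a model that conditions on baseline, a covariate main effect acts on the follow-up outcome directly. In this model baseline is on the left-hand side, so a covariate without a time interaction shifts all three visits by the same amount. A site or sex difference that is absent at baseline and appears only after treatment does not have that shape. Aim 1 is about improvement, treatment is hands-on therapy at three sites, and the plan justifies stratifying by sex by reported sex differences in pain conditions. Differences in improvement by site or sex are therefore possible, though the documents do not claim them.

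At stake is a small amount of power on both primary outcomes, and how far a chance imbalance between arms in site is corrected. The two specifications also give different standard errors and p-values, so the plan should leave no doubt which is primary.

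**Working it through.** The documents state no power, SD, correlation, effect size or dropout, so there is no figure of the plan to reproduce.

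**Inputs from the documents:** 180 participants, 1:1 (90 per arm), three sites, three visits, two-sided 5% tests.

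**Assumed, not in the documents:** SD 14 at baseline and 16 later; correlation 0.6 between all visits; equal sites; half women; complete data; a 5.5-point Quebec effect; improvement differing by 4 points by sex and 3 per step between sites (smaller case), or 6 and 4 (larger case).

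**1. With time interactions, or with no gaps.** The 8-week contrast has residual variance 16² × (1 − 0.6²) = 163.84. SE = √(163.84 × 2/90) = 1.91.

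**2. Main effects only.** Let v = (0, 1, 1) be the pattern of a gap in improvement over the visits. One shared coefficient captures a fraction f = (1′Wv)/(1′W1) of it, where W is the inverse covariance matrix. The column sums of W are 0.003188 (baseline) and 0.001395 (each later visit), so f = 0.00279/0.005978 = 0.467. The model then misfits by −f at baseline and 1 − f afterwards, and the misfit enters the residual covariance. With V = 0.25 × (sex gap)² + (2/3) × (site step)²:

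- Baseline variance: 196 + f²V
- 8-week variance: 256 + (1 − f)²V
- Covariance: 134.4 − f(1 − f)V

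| Case | V | Conditional variance | Reported SE |
|---|---|---|---|
| No gaps | 0 | 163.84 | 1.91 |
| 4 and 3 points | 4 + 6 = 10 | 258.84 − 131.91²/198.18 = 171.04 | √(171.04 × 2/90) = 1.95 |
| 6 and 4 points | 9 + 10.67 = 19.67 | 261.59 − 129.51²/200.28 = 177.85 | √(177.85 × 2/90) = 1.99 |

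Simulation of the same set-up with sex-stratified randomisation (8,000 replicates) agrees: 1.946 against 1.909 with time interactions, and 1.987 against 1.911. Variance ratios are (1.946/1.909)² = 1.04 and (1.987/1.911)² = 1.08. Simulated power goes from 80.8% to 82.1% and from 78.8% to 81.1%. Type I error was 4.8% to 5.4% across versions.

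**3. Reported SE or real precision?** This depends on what was stratified. With site and sex both stratified (2,000 replicates), the actual spread of the estimate was the same under both models: 1.932 against 1.931 in the smaller case, 1.947 against 1.945 in the larger. Only the reported SE differed: 1.94 against 1.90, and 1.98 against 1.90. The loss there is a slightly conservative test. If only sex was stratified, chance site imbalance also adds some real variance under main effects.

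**4. A fixed site imbalance.** Suppose HIP+/SFR numbers at the three sites are 24/36, 30/30 and 36/24. Coding the sites −1, 0, 1, the arms differ in mean site code by 12/90 − (−12/90) = 0.267. A 5-point step then gives an unadjusted error of 0.267 × 5 = 1.33 points. Known-covariance calculations (SD 15 at every visit) give the 8-week error:

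| Site difference (5 points per step) | Correlation | No covariates | Main effects | With time interactions |
|---|---|---|---|---|
| Constant level | 0.4 / 0.6 / 0.8 | 0.80 / 0.53 / 0.27 | 0 | 0 |
| Improvement | 0.4 / 0.6 / 0.8 | 1.33 | 0.81 / 0.99 / 1.16 | 0 |

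Main effects remove all of the first kind. Of the second they leave 0.81/1.33 = 61% to 1.16/1.33 = 87%, so they absorb 13% to 39%.

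**The case against.** **The text does not rule out time interactions.** It lists none, but the same paragraph uses the term fixed effects for an interaction too. This stands as a limit. Main effects remain the natural reading, because the group*time term is spelled out and these are not.

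**The effect is small and driven by assumptions.** This also stands. Steps of 3 to 4 points mean 6 to 8 points between the extreme sites, more than the 5.5-point treatment effect assumed. With half the smaller gaps (2 and 1.5 points) the power gain is at most about 0.4 percentage points. The documents also reduce the scope for site differences by training therapists and fixing the treatment components, their minutes and the number of visits.

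**Stronger readings that the documents do not support.**

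- A reader might infer that the site and sex terms do no adjusting, or act mainly at baseline. A constant shift acts equally at every visit, removes level differences completely and absorbs part of the rest.
- A reader might infer bias or excess false positives. With complete data, randomisation keeps the contrasts unbiased whichever covariates are used, and simulated type I error stayed near 5%.
- A reader might infer that chance site imbalance goes uncorrected. That is wrong for level differences and only partly right for improvement. It also presupposes that site was not stratified, which the analysis section contradicts.
- A reader might infer that the precision bought by stratifying is lost. With both factors stratified the estimate is as precise under either model; only its reported SE is larger.

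One route to bias exists. With dropout made to differ by site and arm and no true effect, simulated bias was −0.43 and −0.73 points with main effects (3- and 6-point site steps), against −0.08 and −0.02 with time interactions. Nothing in the documents says such dropout is expected.

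**Conclusion.** The point holds as a minor gap in specification. As naturally read, the model adjusts fully for constant site and sex differences and only partly for differences in improvement. The analysis is valid without the change, and at worst slightly conservative.

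On the assumed values, time interactions save about 4% to 8% of variance, equivalent to about 180 × 0.04 = 7 to 180 × 0.08 = 14 participants, and add about 1 to 3 percentage points of power. If improvement does not vary by site or sex, the gain is nil and the cost negligible. The structural conclusion follows from the model text. Its size rests wholly on the assumed SDs, correlation and gaps, none of which the documents give. The consequence also depends on whether site was a randomisation stratum, on which sections 6 and 10 differ.

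**What to change.** In the Aim 1 paragraph of section 10, list the fixed effects as time, group*time, site, sex, site*time and sex*time. Apply this to both primary outcomes and to the secondary outcomes analysed the same way. The treatment contrasts at 8 weeks and 6 months keep their meaning, and the baseline constraint on the arms is unaffected.

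The extra parameters number (3 − 1) × 2 = 4 for site and (2 − 1) × 2 = 2 for sex, six in all, which 180 participants carry easily. The change is one line of plan and of code, with no new data. Make it before outcomes are seen by arm. In the same edit, reconcile the Design and Randomization Plan with the analysis section on whether site was a stratification factor; the time interactions are worth having either way.

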- Any recurrence of previously resolved condition whether or not it is related to the study treatment or procedure.
- Any clinically significant findings from the study-related or non-study related procedures such as vital sign measurements, physical exams and any other procedures.

A serious adverse event will be considered one that:

- Results in death
- Is life threatening, or places the participant at immediate risk of death from the event as it occurred

- Requires or prolongs hospitalization
- Causes persistent or significant disability or incapacity
- Is another condition which investigators judge to represent significant hazards

After consent and prior to randomization, only adverse events that are a direct result of study procedures determined by the site principal investigator (PI) or occur while the participant is under study staff supervision will be recorded. Examples of AEs that will be tracked prior to randomization include (but not limited to): falls during the functional testing or emotional distress caused by the questionnaires. Following randomization, all AEs, regardless of relationship to study procedures, will be collected until the end of the study.

Secondary Outcome Measures

Self-Report Measures

1. Research Task Force (LBP) Impact Score⁴³: This will be used to assess the personal impact of LBP. Impact is defined as a combination of pain intensity, pain interference with normal activities and function, using 9 items from the 29-item PROMIS short form (score range: 8-50). NOTE: This questionnaire will also be used as part of inclusion/exclusion screening.
2. Low Back Activity Confidence Scale: A relatively new questionnaire that measures a person's confidence in their ability to perform 15 different activities, including carrying, pushing, sitting, walking, and exercising, that may be directly affected by low back pain. Reliability and validity has been previously established.⁴⁴

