The Principal Investigator ([name]), along with the site PI's, will be responsible for ensuring participants' safety on a daily basis. The *Data and Safety Monitoring Board (DSMB)* will act in an advisory capacity to the NIA Director to monitor participant safety, evaluate the progress of the study, to review procedures for maintaining the confidentiality of data, the quality of data collection, management, and analyses. The DSMB will have a Safety Officer (SO); the SO will not be involved in the study in any other way. The DSMB reviewed and approved the study protocol on 8/19/2019 (i.e. prior to initiation of enrollment). The PI will be informed of serious adverse events as soon as they occur and will notify the NIA and DSMB within 24 hours of notification. The *DSMB* will meet twice annually by teleconference call to review study progress, data quality, and participants' safety.

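### The only safety-analysis rule applies a >10% frequency filter, with no stated denominator, to serious adverse events, and no by-arm SAE summary is exempt from it

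*Combined protocol and SAP*

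**What the plan says.** Section 10 (Data), in the statistical analysis under Aim 1, devotes one sentence to safety. It names "The rates of individual adverse events and serious adverse events that occur >10" per cent, together with "adverse events classified by organ system and relatedness will be calculated for each group", and says these will be "compared using Chi-square or Fisher's exact tests". No base is given for the 10%: it could be one arm, either arm or both arms together, and participants or events.

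Other parts of the protocol bear on the point:

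- Section 6, Adverse Events: "Following randomization, all AEs, regardless of relationship to study procedures, will be collected until the end of the study". An event is serious if, among other criteria, it "Requires or prolongs hospitalization".
- Section 8, on the Data and Safety Monitoring Board (DSMB): the principal investigator is told of SAEs as they occur and "will notify the NIA and DSMB within 24 hours of notification". The board meets twice a year.
- Section 10, Reporting: publications, presentations and a registry description of the trial are promised, with no safety table specified.

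**The concern.** A frequency cut-off is a normal way to keep a table of common adverse events short. Its usual scope is non-serious terms, because serious events are expected to be few and each one matters. Here the cut-off comes straight after the words for serious adverse events, and it governs what is calculated as well as what is tested. Followed literally, the plan would give no by-arm figure for an SAE type seen in, say, 8 of 90 participants in one arm and none in the other.

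The data will exist, since every event after randomization is collected. What is missing is a rule that turns them into a comparison of serious events between arms. Such events would still enter the organ-system and relatedness tables, but mixed with non-serious events. Notification of the NIA and the DSMB is oversight while the trial runs, and it does not commit the final analysis to a by-arm SAE table.

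The undefined denominator adds to this, because the same data can pass or fail depending on which base an analyst picks.

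**Working it through.** The plan gives no expected SAE rate and no safety calculation, so there is no stated figure to reproduce. The check reads the sentence first and then works out what the filter does.

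**Reading.** The qualifier can attach to both nouns or only to the nearer one, which is the serious events. SAEs are filtered either way. If serious events are meant as one class and not as separate types, the class as a whole is filtered.

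**Inputs.** Total sample 180 and equal allocation (Section 6, Design and Randomization Plan), so 180/2 = 90 per arm. Two-sided 5% tests (Section 10, Statistical Analysis; no separate level is stated for adverse events). Fisher's exact test, one of the two the plan names. SAE rates are assumptions.

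**Count needed to pass.** More than 10% means floor(0.10 × n) + 1:

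- Per arm: 0.10 × 90 = 9, so at least 10 (10/90 = 11.1%).
- Pooled: 0.10 × 180 = 18, so at least 19 (19/180 = 10.6%).

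The base matters: 10 vs 0 passes per arm (11.1%) but fails pooled (10/180 = 5.6%).

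**Splits that stay below the filter** (two-sided Fisher, 90 per arm):

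| Split | p | Below which filter |
|---|---|---|
| 6 vs 0 | 0.029 | per arm and pooled |
| 7 vs 0 | 0.014 | per arm and pooled |
| 8 vs 0 | 0.007 | per arm and pooled |
| 8 vs 1 | 0.034 | per arm and pooled |
| 9 vs 0 | 0.003 | per arm and pooled |
| 9 vs 1 | 0.018 | per arm and pooled |
| 12 vs 3 | 0.028 | pooled only |
| 14 vs 4 | 0.023 | pooled only |
| 18 vs 0 | 0.000003 | pooled only |

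Near misses: 5 vs 0 (p = 0.059), 7 vs 1 (0.064) and 9 vs 2 (0.057) do not reach 5%.

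**Chance that an SAE type passes**, for an assumed true rate π that is equal in both arms. Pooled = P(Bin(180, π) ≥ 19). Either arm = 1 − [1 − P(Bin(90, π) ≥ 10)]².

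| π | Pooled | Either arm |
|---|---|---|
| 3% | 0.0002% | 0.08% |
| 5% | 0.2% | 2.9% |
| 8% | 13% | 33% |
| 10% | 44% | 65% |

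At 5%, for example, P(Bin(90, 0.05) ≥ 10) = 0.0145, and 1 − (1 − 0.0145)² = 0.029.

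**Power of the test itself.** This is the exact probability that Fisher's test is significant, and the probability that it is significant while both arms stay under 10 cases:

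| Assumed rates | Power | Significant and below the per-arm filter |
|---|---|---|
| 2% vs 1% | 0.4% | 0.4% |
| 3% vs 1% | 2.4% | 2.4% |
| 5% vs 1% | 15% | 13.8% |
| 8% vs 1% | 49% | 31.6% |

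At 5% vs 1%, then, nearly all the splits that the test would flag are ones the filter leaves out.

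**The case against.** The strongest reply is that the sentence is loosely worded and not a deliberate rule. The authors may have meant the cut-off for common individual terms, with serious events handled as a class. The plan also states what will be calculated and does not say that rarer serious events will be suppressed. That may be the intent, but the text does not say it: the qualifier is next to the serious events, and on the class reading they are still filtered.

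A second reply is that the denominator is less open than it looks. Rates are to be calculated for each group, and the named tests presuppose participants as the unit. This largely disposes of the question of participants or events. It does not settle whether the screen applies per arm, in either arm or pooled.

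A third is that little inference is at stake. The intervention is described as minimal risk, no SAE rate is given, and at 3% vs 1% a significant result hidden by the filter has a probability of only 2.4%. The listed splits show what the test would do at 90 per arm and do not predict what will happen. This stands, and it means the loss at low rates is mainly descriptive. It does not defend the filter: the rarer serious events are, the more completely a 10% cut-off removes them.

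Finally, how far an imbalance would be diluted in the unfiltered tables depends on non-serious counts that the documents do not give. That is fair. The dilution cannot be sized, but serious events are not identifiable as such in those tables.

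**Conclusion.** The concern holds. As written, the plan calculates and compares SAEs by group only above an undefined 10%, and nothing elsewhere in the protocol supplies a by-arm summary of serious events at any frequency. At assumed equal rates of 5% or less, an SAE type would almost never get its own by-arm figure (at most 2.9% of the time). Imbalances that the plan's own test would flag, up to 9 vs 0 on a per-arm reading or 18 vs 0 on a pooled one, fall outside the specified serious-event analysis.

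This rests on 90 analysed per arm, on the natural reading of one sentence, and on assumed SAE rates. It does not show that serious events go uncollected or unreported to the DSMB, and it touches no efficacy result. The change should be made because following the rule gives a poorer account of harm and correcting it is cheap. The missing denominator alone would be only a point of clarification.

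**What to change.** Rewrite the sentence so that the >10% filter applies only to individual non-serious adverse event terms, and state its base: participants, and whether per arm, in either arm or pooled. Add that the number and percentage of participants with any SAE, and with each SAE type, will be reported by arm at any frequency. Compare any SAE between arms with Fisher's exact test. A risk difference with an exact 95% confidence interval is optional. If only the descriptive gap is to be closed, the unfiltered by-arm table alone does most of the work.

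The cost is one sentence and one table from data already collected, with no change to data collection, treatment or the efficacy analyses. The downside is sparse rows, wide intervals and low power for rare events, so the table should be read mainly as description.
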